PCS	Potentially Clinically Significant
PT	Preferred Term
SMQ	Standardized MedDRA Queries
SOC	System Organ Class
SAE	Serious Adverse Event
SAP	Statistical Analysis Plan
SBP	Systolic Blood Pressure
TEAE	Treatment Emergent Adverse Event
TESAE	Treatment Emergent Serious Adverse Event
TLF	Table, Listing, and Figure
ULN	Upper Limit of Normal, value provided by the laboratory
WHODD	World Health Organization Drug Dictionary
WHO	World Health Organization

1 INTRODUCTION

The study was terminated by Sponsor on February 19, 2021. Twenty-two subjects were randomized for the study at the study termination. This statistical analysis plan (SAP) provides a more detailed elaboration of the analyses.

2 STUDY OBJECTIVE

To assess the efficacy and safety of intravenous pamrevlumab, an investigational monoclonal antibody against connective-tissue growth factor (CTGF), compared to placebo, in hospitalized patients with acute COVID-19 disease due to confirmed SARS-CoV-2 infection.

3 STUDY DESIGN

This is a randomized, double-blind, placebo-controlled phase 2 study of the efficacy and safety of intravenous pamrevlumab, a monoclonal antibody against connective-tissue growth factor (CTGF), in hospitalized subjects with acute COVID-19 disease due to SARS-CoV-2 infection.

Eligible subjects are those with documented SARS-CoV-2 infection, age 40 to 85 years, with evidence of respiratory compromise requiring hospital admission. This age range is chosen to enhance detection of potential clinical benefits in subjects at highest risk for developing severe COVID-19 disease in this proof-of-concept study.

The total sample size is approximately 130 subjects. Subjects are randomized in a 1:1 ratio, according to a pre-determined randomization list from a permuted block design, to receive either pamrevlumab or placebo. All subjects are treated with standard-of-care according to the judgment of the Investigator.

Study drug is administered as IV infusion on Days 1 (day of randomization), 7, 14 and 28. A follow-up visit is performed 4 weeks after the last dose.

4 ENDPOINTS

4.1 Primary Efficacy Endpoint

The primary endpoint is the proportion of subjects who never received mechanical ventilation and/or ECMO and alive at Day 28.

4.2 Secondary Efficacy Endpoints

- Proportion of subjects alive, discharged home, and not on supplemental oxygen at Day 28
- Proportion of subjects who never received mechanical ventilation and/ or ECMO and alive at Day 14
- Time to recovery by Day 28 based on the NIAID 8-point ordinal scale (Day of recovery is defined as the first day on which the patient satisfies one of the following three

categories from the ordinal scale: (1) Not hospitalized, no limitations on activities; (2) Not hospitalized, limitations on activities and/or requiring home oxygen; (3) Hospitalized, not requiring supplemental oxygen, no longer requiring medical care (used if hospitalization was extended for infection-control reasons)

- Clinical status based on the NIAID 8-point ordinal scale (time range: Days 1 to 28)
- Days in ICU/CCU (either on or off mechanical ventilation and/or ECMO) at Day 28
- Days on mechanical ventilation and/or ECMO at Day 28
- Time to mechanical ventilation/ECMO or all-cause mortality at Day 28
- All-cause mortality at Day 28 (proportion of subjects deceased)
- Time to death from any cause at Day 28
- Change in $\text{PaO}_2/\text{FiO}_2$ ratio as categorical variable using Berlin criteria for ARDS categorization (mild, moderate, severe) (time range: Days 1 to 28)
- Change in $\text{PaO}_2/\text{FiO}_2$ ratio as continuous variable (time range: Days 1 to 28)
- Change in resting SpO_2 adjusted by FiO_2 (time range: Days 1 to 28)
- Change in (non-invasive) oxygen supplementation requirements (time range: Days 1 to 28)

4.3 Safety Assessments

Treatment-emergent adverse events (TEAEs); treatment-emergent serious adverse events (TESAEs), including hypersensitivity/ anaphylactic reactions, and vital signs.

5 GENERAL STATISTICAL CONSIDERATIONS

All data collected will be included in the data listings. All analyses will be performed using SAS® Version 9.3 or higher.

5.1 Statistical Methodology

There will be no treatment comparison analysis performed for this early terminated study.

Baseline is defined as the last value on or before the first infusion.

Continuous variables will be summarized using descriptive statistics: n, mean, standard deviation (SD), standard error (SE), median, 25th and 75th percentile, minimum, and maximum. The 2-sided 95% confidence interval for the treatment group mean will be presented as appropriate. Categorical variables will be tabulated by frequency count and percentage. The confidence interval for the proportions for each treatment group will be calculated using the Clopper-Pearson method as appropriate.

The Clopper-Pearson exact 95% CIs for the dichotomous parameters will be from SAS FREQ procedures with option BINOMIAL (EXACT). The 95% CIs for means of normally distributed parameters will be from appropriate SAS procedures such as PROC MEANS.

Analyses will be performed using SAS® Version 9.3 or higher.

5.2 Analysis Populations

The study population is defined through inclusion/exclusion criteria to reflect the targeted patient population for study. The details of the inclusion/exclusion criteria can be found in the protocol.

5.2.1 Intent-to-Treat (ITT) Population

The ITT population is defined as all randomized subjects. Subjects will be analyzed according to the treatment as randomized.

5.2.2 Safety Population

The safety population is defined as all subjects who have received any study medication. Subjects will be analyzed according to the treatment as received.

5.3 Data Handling Rules and Presentation Specifications

The following general guidelines will apply to all statistical analyses and data presentations:

- Age (Years) = INTCK('YEAR', Birth Date, Date of Informed Consent,'C') where INTCK is a SAS function. Age groups are 18 to 64, 64 to 75, >=75
- Duration of Ventilation will be calculated as Ventilation Stop Date/Time – max(Ventilation Start Date/Time, Randomization Date [we will use 12:00 if no time available] or 1st Dose completion Date/Time)
- All reporting values (mean, SD, 95% CI, etc.) for continuous variables will have the same decimal places as the raw data.
- All percentages will be rounded to one decimal place and lined up by the decimal place. The percentage will be suppressed when the count is zero. All analysis statistics will have the same decimal place as the raw value. All duration of time will have 1 decimal place.
- Body weight, height and temperatures will be converted using the following formula:
 - kg = lb/2.2
 - cm = 2.54 x in
 - °C = (5/9) x (°F – 32)
- Computation formulas:
BSA = [Weight ^{0.425} (kg) * Height ^{0.725} (cm)] x .007184
BMI = Weight (kg) / (Height (m))²

- Mean Arterial Pressure (MAP) will be derived using the following equation:
$$\text{MAP} = (2/3) * \text{DBP} + (1/3) \text{ SBP}$$
- For continuous variables that are recorded as “ $<\text{X}$ ” or “ $>\text{X}$ ”, the value of “ X ” will be used in the calculation of summary statistics.
- All tables and listings will have a header showing “FibroGen, Inc.”, the protocol number, date of the database transfer, and Page x of y. A footer will show the program file path/name, output file path/name, run date and run time.

6 SUBJECT ACCOUNTABILITY AND DISPOSITION

The number and percentage of subjects who are randomized, dosed, treatment prematurely discontinued, and completed the study will be summarized by treatment group. Reasons for premature discontinuation as recorded on the Study Disposition page of the CRF will be summarized.

7 DEMOGRAPHICS AND BASELINE CHARACTERISTICS

7.1 Demographics and Important Baseline Characteristics

Demographic parameters and important baseline characteristics will be summarized for ITT population by treatment arm. These include but are not be limited to age, age group, sex, ethnicity, race, weight, body-mass index (BMI), smoking status, and selective medical history.

Descriptive statistics (n, mean, standard deviation, median, 25-75th percentiles, minimum, and maximum) will be presented for continuous variables. Frequency distributions (number and percentage of subjects) will be presented for categorical variables.

Descriptive statistics of baseline efficacy assessments will be presented in their change from baseline tables.

7.2 Medical History

Medical history will be listed for the Safety population.

8 TREATMENTS AND MEDICATIONS

8.1 Prior and Concomitant Medications

The use of the prior and concomitant medications will be listed for the ITT population. The version of WHODRUG used to code the medication is stated in the data management plan (DMP).

Medications are classified into 2 categories:

1. Prior medications - medications that are stopped prior to the first study drug infusion

2. Concomitant medications - medications that are used concomitantly with the study drug, which includes all medications that started after or not stopped before the first infusion.

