6.3. Concomitant Medications, Supplemental Oxygen Needs, and other Care

Subjects will be treated according to best available standard-of-care according to the judgment of the Investigator. All concomitant medications, including approved and non-approved treatments for COVID-19 (e.g., hydroxychloroquine, IL-6 inhibitors, etc.), as well as supplemental oxygen needs, will be collected and recorded.

In addition, the following will be recorded and collected: documentation of SARS-Cov-2 infection, documentation of any other infection(s) prior to or during hospitalization, and whether or not aggressive care is withheld or withdrawn, including the reason for withholding or withdrawal of care (e.g., DNR/DNI order, resource limitation). Vital status may also be obtained from public records.

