APPENDIX I HANDLING MISSING/INCOMPLETE DATES

A. Handling Missing/Incomplete AE Onset Date

If the AE onset date is incomplete or missing, the following rules will be applied to impute AE onset date.

- If year and month are present, only day is missing,
 - a) If AE onset Year/month = Day 1 Year/month, assign onset day = day of Day 1 (Day 1 is the first infusion day);
 - b) If AE onset Year/month \neq Day 1 Year/month, assign onset day = 1st of the month;
- If year is present, month and day are missing, or when only month is missing (treating day as missing),
 - a) If AE onset year = year of Day 1, assign onset date = month and day part of Day 1 date;
 - b) If AE onset year \neq year of Day 1, assign onset date= January 1st.
- If onset date is completely missing, assign onset date = date of Day 1.

If the stop date is complete and the imputed start date as above is after the stop date, the start date will be imputed by the stop date.

B. Handling Missing/Incomplete Prior or Concomitant Medication Start/Stop Dates

For prior or concomitant medications, including rescue medications, incomplete (i.e., partially missing) start date is imputed the same way as for the AE described above. When the start date and the stop date are both incomplete for a patient, impute the start date first.

Incomplete Stop Date

The following rules are applied to impute the missing stop date, if needed.

- If year is present, month and day are missing, or when only month is missing (treating day as missing)
 - a) If stop year = year of last dose, assign stop date = month and day of the last dose date;
 - b) If stop year \neq year of Day 1, assign stop date= December 31st.
- If year and month are present, only day is missing,
 - a) If AE stop Year/month = Year/month of last dose date, assign stop day = day part of last dose date
 - b) If AE stop Year/month \neq Day 1 Year/month, assign onset day = last day of the month;
- Impute CM end date even if 'ONGOING' is checked so as to report the CM treatment duration in the study if needed.

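### The partial stop-date rule for medications in SAP Appendix I.B uses two different anchors, so some stop dates get no value and others get two; secondarily, COVID-19 co-treatment is listed but not tabulated by arm

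*SAP*

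**What the plan says.** **Co-treatment.** SAP section 3 leaves background therapy open: "All subjects are treated with standard-of-care according to the judgment of the Investigator". Protocol 6.3 expects a wide range of drugs and records them all: "All concomitant medications, including approved and non-approved treatments for COVID-19 (e.g., hydroxychloroquine, IL-6 inhibitors, etc.), as well as supplemental oxygen needs, will be collected".

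**Presentation.** SAP 8.1 plans a listing only: "The use of the prior and concomitant medications will be listed for the ITT population". It defines two classes. Prior drugs are those stopped before the first infusion. The concomitant class is the remainder, "which includes all medications that started after or not stopped before the first infusion". SAP 7.1 gives an open-ended set of baseline characteristics to be tabulated by arm and does not name COVID-19 therapy among them.

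**Date rules.** Appendix I.B applies "For prior or concomitant medications, including rescue medications", which is the only place in the SAP where rescue medication is mentioned. For a stop date with the day missing, branch (a) reads: "If AE stop Year/month = Year/month of last dose date, assign stop day = day part of last dose date". Branch (b) applies when the stop month differs from the month of Day 1, and says "assign onset day = last day of the month". The pair of rules for a missing month is built the same way: (a) tests the year of the last dose, (b) the year of Day 1.

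**Context.** SAP section 1 reports 22 subjects randomized before termination. SAP section 5 puts all collected data into listings, and SAP 5.1 rules out any treatment comparison.

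**The concern.** Two branches that are meant to be alternatives must test the same condition. Here one tests the last dose and the other tests Day 1, so they are complementary only when both fall in the same calendar month (or year). The references to an AE stop and an onset day, inside a rule for medication stop dates, suggest text carried over from the adverse-event rule. A programmer cannot implement the rule as written without making an undocumented choice.

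The stop date decides whether a drug already started by the first infusion is prior or concomitant under SAP 8.1.

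The second matter is presentation. Co-treatment is the investigator's choice, the protocol names no stratification factor, and the covariate-adjusted models of Protocol 9.4 have given way to descriptive summaries. The concomitant class combines a drug already running at the first infusion, which describes baseline, with a drug started later, which may be a response to worsening. No by-arm table separates the two.

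**Working it through.** The documents give no figure for partial stop dates or for co-medication use, so there is no planned number to reproduce.

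**1. The two branches, day missing.** Let M1 be the month of Day 1, ML the month of the last dose, and S the known stop month.

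| Case | S | Branch (a): S = ML | Branch (b): S ≠ M1 | Result |
|---|---|---|---|---|
| M1 = ML | S = M1 | yes | no | one date |
| M1 = ML | other | no | yes | one date |
| M1 ≠ ML | S = M1 | no | no | no date |
| M1 ≠ ML | S = ML | yes | yes | two dates |
| M1 ≠ ML | other | no | yes | one date |

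**2. Examples.**
- Day 1 on 20 January 2021 puts Day 28 on 16 February (20 January + 27 days). A stop in January with no day meets neither branch. A stop in February meets both and gets 16 February and 28 February.
- Day 1 on 2 January puts Day 7 on 8 January. If that is the last dose, a drug started on 12 January and stopped in January gets 8 January, four days before it started. The appendix's order check covers only an imputed start against a complete stop date, so it does not catch this.
- Year-only version: Day 1 on 20 December 2020, last dose 16 January 2021. A stop in 2020 gets no date. A stop in 2021 gets both 16 January and 31 December 2021, the latter after the SAP's own approval date of 3 May 2021.

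**3. How often M1 and ML differ.** For a last dose on Day 28 the months agree only if Day 1 falls on or before (month length − 27): 4 dates in a 31-day month, 3 in a 30-day month, 1 in February.
- Full year: 7×4 + 4×3 + 1 = 41 dates agree, so 365 − 41 = 324 differ; 324/365 = 88.8%.
- From Amendment 1.0 (12 May 2020) to termination (19 February 2021): 254/284 = 89.4%.
- Ending on 23 January 2021, so that Day 28 is reached by termination: 228/257 = 88.7%.
- Outpatient Day 28 window of ±3 days: 288/365 = 78.9% (Day 25) to 358/365 = 98.1% (Day 31).
- Last dose Day 14: 12×13/365 = 156/365 = 42.7%. Day 7: 12×6/365 = 72/365 = 19.7%. Day 1 only: 0%.
- Years differ (full course): 27/365 = 7.4%, or 27/257 = 10.5% in the shorter window.

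**4. What a partial date meets.** Assume a full course, Day 1 uniform over the 257 dates, and a true stop uniform over Days 1 to 28 with the day lost. Then 44.4% of stop dates match neither branch, 44.3% match both and 11.3% get one date. With both branches referring to the last dose, the first two shares become 0%.

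**5. Consequence for class.**
- *Two dates:* ML lies after M1, so both dates follow the first infusion and the drug is concomitant either way. Only duration changes, by 12 to 16 days on average and at most 30, depending on the assumed range of stop dates.
- *No date:* a drug started on or after the first infusion is concomitant by its start date. The class is undetermined only for a drug started before it.

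**6. Chance imbalance in co-treatment.** Assume 11 subjects per arm and K users of a drug among 22. The users in one arm, X, are hypergeometric and the arm difference is 2X − K. For K = 11: P(|2X − 11| ≥ 3) = 1 − 2×462×462/705,432 = 39.5%. For even K the difference is even, so 3 or more means 4 or more (36 points rather than 27): 9.0% for K = 4, 14.9% for K = 6 or 16, and 18.3% for K = 8 or 14. The figures for odd and even K therefore rest on different effective thresholds.

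**The case against.** The case for leaving the plan alone has real force. The stop-date rule is invoked only if needed, for incomplete dates. Medications are scheduled for daily recording while the subject is in hospital, so there may be few such dates, or none. No analysis of medication duration is specified, so the two-date cases change no planned output. A listing keeps each record separate, all data are listed, and with 22 subjects co-treatment can be counted by hand if arm and start date are shown. The protocol promises collection of these drugs and no by-arm table, so nothing promised has been dropped. Chance imbalance comes from the sample size; a table would show it but not remove it.

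Most of this stands, and it rules out two stronger readings. A reader might infer from the 89% that the rule fails for most full-course subjects. That figure counts possible Day 1 dates, not subjects. It says nothing about how many stop dates are incomplete, and the documents do not say how many subjects completed the course. A reader might also infer that the outcome tables cannot be read against background therapy. The listing makes that possible, though SAP 8.1 does not specify its columns, and start dates, which separate background from later use, are untouched by the stop-date error.

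What does not stand is that the rule is therefore acceptable. It is a stated derivation that gives no answer, or two, under an ordinary schedule.

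**Conclusion.** The partial stop-date rule is wrong as written and should be corrected. When a stop date is incomplete and Day 1 and the last dose fall in different months, a stop in the Day 1 month has no imputed date and a stop in the last-dose month has two. The first leaves the prior/concomitant class open for drugs started before the first infusion; the second affects duration only. Separately, an imputed stop can precede a known start. The condition on months holds for about 89% of possible full-course Day 1 dates, about 43% with a last dose on Day 14 and about 20% on Day 7, taking Day 1 as uniform over the calendar. The number of records affected is unknown and could be zero.

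The lack of a by-arm co-treatment table is a lesser point. The imbalance figures rest on an assumed 11:11 split and assumed user counts. With no treatment comparison planned, the effect of both matters is confined to descriptive reading.

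**What to change.** **Appendix I.B (main change).**
- Use the last-dose month in both day-missing branches: equal to it, assign the last-dose day; otherwise, month end. Do the same with the last-dose year when the month is missing. Each partial stop date then meets exactly one branch.
- Never impute a stop before the start date, or after death or study end.
- Replace the adverse-event and onset labels with medication stop date and stop day.

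The cost is a few lines of SAP text and one derivation. One consequence should be stated: a drug begun before the first infusion and stopped in the Day 1 month, day unknown, will be classed as concomitant even if it had in fact stopped earlier.

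**SAP 8.1 (secondary).** Add a small by-arm ITT table of COVID-19-directed drug classes with two columns: ongoing at the first infusion, and first started after it. Label the second as post-randomization and not a covariate. Drugs stopped before the first infusion stay under prior. Flag start dates imputed to Day 1. The data are already collected and coded, so this costs one table; its drawback is small cells.

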8.2 Study Drug Exposure

Duration of study drug exposure in days is calculated as: (last dose date – first dose date + 1). Duration of study drug exposure will be summarized as a continuous variable. The duration will also be tabulated by the following categories for the Safety population.

- 1 to 3 days
- >3 to <=7 days
- >7 to <=14 days
- >14 days <=21 days
- >21 days

Pamrevlumab infusion dose (in mg and mg/Kg), number of infusions during study, and interruptions during infusion and reason for interruptions will also be listed.

8.3 Compliance

The compliance will be presented as % of actual doses of infusion administered over the expected total dose of infusions during study for the safety population. That is, compliance = actual doses received / scheduled doses * 100%. Treatment compliance will be listed only.

9 EFFICACY ANALYSES

Efficacy data will be summarized descriptively based on observed data for the ITT population. There will be no imputation performed for the missing endpoint value.

9.1 Primary Efficacy Endpoint - Proportion of Subjects who Never Received Mechanical Ventilation and/or ECMO and Alive at Day 28

Proportion of subjects never received mechanical ventilation and/or ECMO and alive at Day 28 will be summarized based on observed data.

9.2 Proportion of Subjects Alive, Discharged, and not on Supplemental Oxygen, Proportion of Subjects who Never Received Mechanical Ventilation and/ or ECMO and Alive, and Proportion of Subjects Deceased

Proportion of subjects alive, discharged home, and not on supplemental oxygen at Day 28, proportion of subjects never received mechanical ventilation and/ or ECMO and alive at Day 14, and proportion of all-cause deaths at Day 28 will be summarized descriptively based on observed data.

9.3 Time to Recovery, Time to Mechanical Ventilation/ECMO or All-cause Mortality, and Time to death

- Time (number of days) from randomization to recovery by Day 28 based on NIAID 8-point ordinal scale where recovery is defined as the first day on which the patient satisfies one of the following three categories from the ordinal scale: (1) Not hospitalized, no limitations on activities; (2) Not hospitalized, limitations on activities and/or requiring home oxygen; (3) Hospitalized, not requiring supplemental oxygen, no longer requiring medical care (used if hospitalization was extended for infection-control reasons)

Subjects without the event will be censored at the date of last NIAID 8-point ordinal scale assessment.

- Time (number of days) from randomization to mechanical ventilation/ECMO or all-cause mortality by Day 28

For subjects who did not have the event, the last known assessment date of mechanical ventilation/ECMO use or survival status, whichever later will be defined as the censoring date.

- Time (number of days) from randomization to death from any cause by Day 28

For subjects who are alive, the recorded date of last known alive, last contact date, or the date of the last clinic visit, whichever latest will be defined as the censoring date.

The number of days of the above endpoints will be summarized descriptively as appropriate.

9.4 Clinical Status Based on the NIAID 8-point Ordinal Scale at Day 28

Proportion of subjects by response category on the NIAID 8-point ordinal scale will be summarized descriptively based on observed data at baseline and Day 28.

Order	Ordinal Level
1	Not hospitalized, no limitations on activities
2	Not hospitalized, limitations on activities and/or requiring home oxygen
3	Hospitalized, not requiring supplemental oxygen, no longer requiring medical care (used if hospitalization was extended for infection-control reasons)
4	Hospitalized, not requiring supplemental oxygen, requiring ongoing medical care (COVID-19-related or otherwise)
5	Hospitalized, requiring supplemental oxygen
6	Hospitalized, requiring high-flow oxygen, non-invasive mechanical ventilation, or both

7	Hospitalized, requiring invasive mechanical ventilation, extra-corporeal membrane oxygenation (ECMO), or both
8	Death
Missing	

9.5 Number of Days in ICU/CCU and Number of Days on Mechanical Ventilation and/or ECMO

Total number of days in ICU/CCU (either on or off mechanical ventilation and/or ECMO) at Day 28 and total number of days on mechanical ventilation and/or ECMO at Day 28 will be summarized descriptively.

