9.4. Statistical Methods

The analysis of the proportion of subjects who never received mechanical ventilation and/or ECMO and are alive at Days 14 and 28, the proportion of subjects alive, discharged home, and not on supplemental oxygen at Day 28, proportion of subjects' clinical status based on an 8-point ordinal scale, and proportion of subjects with categorical PaO₂/FiO₂ ratio endpoints will be conducted using logistic regression model with treatment group and adjusting for relevant baseline prognostic covariates.

The number of days in ICU/CCU (either on or off mechanical ventilation and/or ECMO) at Day 28, number of days on mechanical ventilation and/or ECMO at Day 28 will be analyzed using the analysis of covariance (ANCOVA).

Change in PaO₂/FiO₂ ratio to day 28, change in resting SpO₂ adjusted by FiO₂ to day 28, change in (non-invasive) oxygen supplementation requirements to day 28 will be analyzed using Mixed Model for Repeated Measures (MMRM) approach using relevant prognostic factors as covariates and treatment and Time and treatment *time interaction

The analysis will take into account the inter-current events as follows.

1. Treatment discontinuation (e.g., due to AEs, Withdrawal by Subject or Physician Decision): Missing endpoint will be imputed by the last result prior to discontinuation.

- 2. Death: Composite strategy: inter-current event is taken to be a component of the variable. For number of days not requiring mechanical ventilation at Day 14, number of days in ICU/CCU (either on or off mechanical ventilation and/or ECMO) at Day 28, and number of days on mechanical ventilation and/or ECMO at Day 28; days with missing data after death will be imputed with the worst result until Day 28.
- 3. Treatment discontinuation due to recovering and discharged from hospital: Missing endpoint will be imputed with the last result prior to discontinuation.

Treatment comparison analysis of time to event endpoints, will be performed using cox regression model adjusting for relevant baseline prognostic factors. Hazard ratios together with 95% two-sided confidence intervals for the hazard ratio will be provided.

Time to recovery by Day 28, time to mechanical ventilation/ECMO or all-cause mortality by Day 28, and all-cause mortality at Day 28 (proportion of subjects deceased), and time to death from any cause at Day 28 will be analyzed using Cox regression adjusting for relevant prognostics factors. Other methods will be used as appropriate.

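### SAP 9.8 reports every discharged subject as needing no oxygen, and SAP 9.5 neither says how deaths are counted in ICU and ventilator days nor marks the change from protocol 9.4

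*SAP*

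**What the plan says.** SAP 1 states that the sponsor stopped the study with 22 subjects randomized, and SAP 5.1 that "There will be no treatment comparison analysis performed for this early terminated study". SAP 9 then sets the basis for all efficacy summaries: "Efficacy data will be summarized descriptively based on observed data for the ITT population", followed by "There will be no imputation performed for the missing endpoint value".

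**Oxygen.** SAP 9.8 has two categories: no oxygen, and oxygen by nasal cannula or face mask. The first covers subjects breathing room air and also anyone who has left hospital. In protocol Appendix 1, footnote 4 ends the recording of oxygen needs at Day 28 or discharge, whichever comes first. Protocol 9.4 item 3 reads: "Treatment discontinuation due to recovering and discharged from hospital: Missing endpoint will be imputed with the last result prior to discontinuation".

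**Day counts.** Protocol 9.4 item 2 treats death by a composite strategy. For ICU/CCU days and ventilator/ECMO days, "days with missing data after death will be imputed with the worst result until Day 28". SAP 9.5 says only that the ICU/CCU total and the "total number of days on mechanical ventilation and/or ECMO at Day 28 will be summarized descriptively". It does not mention death. SAP 5.3 has a ventilation formula: "Duration of Ventilation will be calculated as Ventilation Stop Date/Time" minus the later of the ventilation start and the randomization date or first-dose completion time, that is, elapsed time. No rule is given for ICU/CCU or ECMO days.

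**The concern.** The 9.8 category gives discharged subjects a favourable value that was not observed, inside a section that says it uses observed data. Someone sent home on oxygen is shown as needing none. The two categories also leave no place for subjects who are dead, ventilated or on ECMO, or on high-flow oxygen or non-invasive ventilation, so the base of the percentage is unclear.

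In 9.5, a by-arm mean still needs a rule for subjects who die, even when the arms are not formally compared. Without one, decedents may be counted on the few days they lived or may be left out. On the first reading, an arm with more early deaths can show fewer ventilator days than an arm whose patients survived after longer ventilation.

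**Working it through.** The plan gives no figure for either summary, so there is none to reproduce. The documents give no death, ventilation or home-oxygen counts. All examples below are assumed, and 11 per arm is an assumption from 22 subjects randomized 1:1.

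**SAP 9.8, texts compared**

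1. SAP 9.8: discharged means no oxygen.
2. SAP 9.4, ordinal level 2: a discharged subject may have activity limits, home oxygen, or both.
3. SAP 9.2: being discharged home and being off oxygen are two separate conditions of one endpoint.
4. Protocol Appendix 1, footnote 4: oxygen needs are not recorded after discharge. The ordinal-scale row is scheduled at Day 28 and does not carry that footnote.

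Item 1 therefore does not fit items 2 and 3, and item 4 means the oxygen-needs record cannot correct it.

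*Size.* If h of n subjects in the base are at home on oxygen at Day 28, the reported proportion is too low by h/n. With n = 11: h = 0 gives 0; h = 1 gives 1/11 = 9.1 points; h = 2 gives 2/11 = 18.2 points.

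*Example.* Of 11 subjects, 5 are home off oxygen, 2 home on oxygen, 1 in hospital on cannula, and 3 dead or ventilated. SAP 9.8 gives 1/11 = 9.1%, or 1/8 = 12.5% if the last 3 are left out. Counting home oxygen gives 3/11 = 27.3%, or 3/8 = 37.5%. The discharge coding costs 18.2 or 25.0 points here. The choice of base moves the figure separately.

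**SAP 9.5, day counts**

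Take ventilation from Day 3 and death on Day d.

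- Elapsed (the SAP 5.3 approach): observed d − 3; protocol rule (d − 3) + (28 − d) = 25.
- Inclusive: observed d − 2; protocol rule (d − 2) + (28 − d) = 26.

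Mean ventilator days with 11 per arm (elapsed, then inclusive):

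| Arm | Observed days kept | Protocol rule |
|---|---|---|
| A: 3 ventilated from Day 3, die Day 5; 8 with none | 3×2/11 = 0.55; 3×3/11 = 0.82 | 3×25/11 = 6.82; 3×26/11 = 7.09 |
| B: 3 survivors ventilated 10 days; 8 with none | 3×10/11 = 2.73 | 2.73 |
| B, variant: 1 such death, 2 survivors ventilated 10 days | (2+20)/11 = 2.00; (3+20)/11 = 2.09 | (25+20)/11 = 4.09; (26+20)/11 = 4.18 |

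Arm A has the lower mean on observed days and the higher mean under the protocol rule, against either form of B. If decedents are left out, A is 0/8 = 0.0.

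Against the three survivors, the order reverses only while d − 3 < 10 (death before Day 13, elapsed) or d − 2 < 10 (before Day 12, inclusive). For death on Day 20, observed means are 3×17/11 = 4.64 or 3×18/11 = 4.91. Both exceed 2.73, so the order is the same either way. Medians are 0 in both arms throughout, since 8 of 11 subjects have no ventilator days.

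The protocol rule has its own oddity: a never-ventilated subject who dies on Day 5 scores 28 − 5 = 23 ventilator days, against 0 observed.

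**The case against.** A reader might infer more than the documents support in five ways.

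- *That the SAP removes the death rule silently.* It does not. The protocol rule is an imputation, and SAP 9 says openly that nothing is imputed. What is missing is a statement that this departs from protocol 9.4, and a reason.
- *That early death must give low counts.* The SAP does not say whether decedents keep their observed days or are excluded. Low counts are one reading.
- *That the SAP's day-count rules conflict.* SAP 5.3 gives an elapsed-time rule for ventilation. The inclusive count in SAP 8.2 is for drug exposure, a different quantity. Only ICU/CCU and ECMO days lack a rule.
- *That 9.8 contradicts protocol 9.4 item 3 for everyone discharged.* Item 3 covers stopping treatment because of recovery and discharge. Under protocol 4.4, discharged subjects are to return on Days 14 and 28 for infusions, so any conflict is limited to those who stop.
- *That home oxygen or death is hidden.* SAP 9.2 separates discharge from being off oxygen, and 9.4 shows level 2. Deaths appear in 9.2, 9.4 and the listing in 10.1.

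It is also fair to say that describing observed days is defensible once the trial has stopped at 22 subjects with no comparison, and that the protocol's score of 23 for a never-ventilated Day 5 death is hard to read by itself. These arguments limit the point. They do not remove the 9.8 misclassification, which follows from the stated category, or the lack of a rule for decedents in 9.5.

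**Conclusion.** Both points stand as minor. The 9.8 point is the firmer: the category misclassifies anyone at home on oxygen at Day 28, against level 2 of the same SAP's scale. The 9.5 point is an unmarked departure from protocol 9.4 and an unstated rule for decedents. Arm means can mislead if decedents keep observed days and deaths come early; medians need not.

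The sizes (9.1 points per home-oxygen subject, and observed means of 0.55 to 0.82 against 6.82 to 7.09 under the protocol rule) rest on assumed counts in an assumed 11 per arm. They show what is possible, not what happened. These are descriptive secondary summaries, and no test or decision is affected.

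**What to change.** **SAP 9.8.** Do not code discharge alone as no oxygen. Use the Day 28 ordinal level: level 1 counts as no oxygen (protocol 3.2 describes the best category as off oxygen); level 2 counts as home oxygen where that is recorded, otherwise unknown. Over all ITT subjects, show dead, ventilated/ECMO, high-flow/non-invasive ventilation and unknown as separate rows.

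**SAP 9.5.** In one table show, per arm, observed days, days under the protocol rule, and deaths. Record the departure from protocol 9.4 and the reason. State how decedents enter the observed count, and give a day-count rule for ICU/CCU and ECMO days.

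**Cost.** The change needs SAP wording, one extra summary line and a few table rows for 22 subjects, with no data collection beyond the schedule. Some cells will read unknown, because level 2 mixes activity limits with home oxygen and because some discharged subjects may have no Day 28 ordinal assessment (Appendix 1, footnote 7 describes their remote visits as covering vital status and safety). There is some overlap with 9.2 and 9.4. Observed days should stay beside the protocol-rule count because of the 23-day oddity.
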